The proposed study is a 28-week randomized, placebo-controlled, double-blind trial comparing the efficacy of ACTH versus placebo for the treatment of fatigue in patients with RMS (RMS). Ninety patients with RMS who meet all of the eligibility criteria will be enrolled from five participating sites. Eligible patients will be consented by site investigators or delegated research personnel before undergoing any study procedures. Subjects will be randomized to ACTH or placebo at 1:1 ratio.

Endpoints

The primary objective of this study is to assess the efficacy of ACTH versus placebo in reducing fatigability in patients with relapsing MS. The primary endpoint is a statistically significant reduction of fatigue measured by MFIS and FSS, which will be administered at baseline, week 8, 16, 24, and 28.

Secondary objectives include assessment of the tolerability and safety of weekly ACTH treatment vs. placebo and evaluation of ACTH on depression, sleepiness, and quality of life measures and the correlations between measures. The secondary endpoints are measured by BDI-II, ESS, SF-36 at baseline, week 8, 16, 24, and 28. Clinical and laboratory adverse events (AE) and serious adverse events (SAE) will be monitored continuously during the study period to capture safety and tolerability information.

Patient Recruitment

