Patients with stable (no relapses for the previous 90 days) relapsing form of MS, being treated with interferon beta1a or 1b, glatiramer acetate, fingolimod, dimethyl fumarate or teriflunomide for at least 6 months, with Expanded Disability Status Scale (EDSS) scores of 4 or less, Modified Fatigue Impact Scale (MFIS) score of 38 or greater, or a Fatigue Severity Scale (FSS) score of 36 or greater, Beck Depression Inventory-II (BDI-II) score of 19 or less, and Epworth Sleep Score (ESS) of 9 or less. Subject will be excluded if he or she has attempted suicide in the past, has current suicidal thinking based on the Columbia Suicide Severity Rating Scale (C-SSr), or is preparing for suicide. History must be negative for difficulty sleeping, sleep apnea, painful nocturnal spasms, nocturnal neuropathic pain, and restless leg syndrome, history of psychosis or neuroleptic use, have no evidence of current hypothyroid state, use of cannabis, opiates, benzodiazepines, or other gaba-ergic medications except baclofen or tizanidine. Subjects cannot have received corticosteroids of any type for 90 days prior to baseline visit. Subjects must not have any of the contraindications for Acthar Gel as listed in the approved label, including sensitivity to proteins of porcine origin. Subject must agree not receive any live or live-attenuated vaccine during the trial. Ninety subjects will be recruited and randomized 1:1 to receive ACTH or placebo in a subject and examining physician-blinded manner. The sample size was calculated by a power analysis for a two-sided test with $\alpha=0.05$ and power = 0.80 and assuming a 20% dropout rate.

Subjects will be randomized in groups of 4, with equal number of placebo and ACTH treated patients in each 4-subject group. In order to reach enrollment target in 12 months, full competitive enrollment will be applied until the enrollment goal is fulfilled.

The study protocol, informed consent forms (ICF), and case report forms (CRF) must be approved by the organization's institutional review board or appropriate ethics committee. Site investigators will obtain written informed consent to participate from eligible patients prior to screening or any study procedures taking place. A copy of the ICF will be given to the patient and the original ICF and the documentation of the consent process will be kept in the patient's record at each site.

Inclusion Criteria

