1. Patient has a relapse during the study. A relapse is defined as a new symptom, or worsening of pre-existing neurologic symptoms, of at least 24 hours duration, in patients who had been clinically stable for the prior 30 days, in the absence of fever, sleep deprivation or severe emotional stress.
2. Patient has an adverse event that presents unacceptable risk judged by the investigator
3. Patient has inadequate adherence to the protocol
4. Patient is lost to follow-up
5. Patient becomes pregnant

Treatment Overview**Dosage and Administration of Acthar® or matching placebo**

The study drug (ACTH 40 units or identical-appearing placebo) will be given subcutaneously twice weekly for 2 weeks. If the patient tolerates this dosage regimen, the dose will be increased to 80 units or placebo twice weekly. If the 80 unit dosage is not tolerated, the dosage will be reduced to 40 units twice weekly for the remainder of the 24 week participation. The weekly doses will be given 3 days apart, for example, on every Monday and Thursday or every Tuesday and Friday. Patients are not allowed to take doses on consecutive days. If a patient cannot take a dose on a scheduled day, the dose can be taken either a day early, or a day late. Patients that forget to take their scheduled dose will be encouraged to take their dose the following day.

Randomization/Treatment assignment and blinding

A total of 90 patients will be randomized either to active drug (ACTH), or placebo in a 1:1 ratio stratified by study site. Each study site will be assigned a site number, and each patient who signed consent form and received a screening test will have a unique study ID, which identifies the patient and the study site at which they participate throughout the study. Within each site, subjects will be randomized in blocks of 4, 2 ACTH and 2 placebo treated patients, to achieve balance in the allocation of subjects to study drug versus placebo arms. The order in which each of the 4 samples is selected will be predetermined by a

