Data forms will be faxed to the data coordination center within 3 business days after each study visit and processed by staff trained in data entry procedures. The forms will be entered by two staff working independently. The completeness of the data and whether the data values are in an appropriate range will be checked periodically. Study sites will be asked to complete data clarification requests for confirmation of missing data or questionable information.

Statistical/Analytical Plan

Primary endpoint

Statistical analysis will be performed to test the change from baseline to end of study in two fatigue measures (MFIS and FSS) to be completed by patient at baseline, Week 8, Week 16, Week 24, and Week 28.

Secondary endpoint

Statistical analysis will be done to test the change from baseline to end of study in depression, sleepiness, and quality of life measures (BDI-II, ESS, and SF-36) to be completed by patient at baseline, Week 8, Week 16, Week 24, and Week 28.

All AEs are to be coded and grouped by organ system. AEs will also be tabulated by severity and by relationship and summarized by treatment group. Summary tables of the AEs will be presented to show the incidence and frequency by treatment group and by study site.

Statistical method

This study will collect longitudinal data that consists of repeated measures on each individual. The mixed-effects regression model for the analysis of longitudinal data will be used to test the changes of the fatigue scores over time.

Sample Size Justification

Ninety subjects will be recruited and randomized 1:1 to receive ACTH or placebo in a subject and examining physician-blinded manner. If the MFIS score decreases from 38 for about 20% with standard deviation =16.4 in the 45 patients who received ACTH, the power to reject the null hypothesis in a paired t-test with alpha=0.5 would be 86%. If the difference of the changes of MFIS score between two treatment group is 7.6 with within group standard deviation=16.4 in the 90 patients, the power to reject the null hypothesis in a t-test with alpha= 0.5 would be 87%. Ziemssen and colleagues (Ziemssen, Hoffman, Apfel, & Kern, 2008) studied the effect of glatiramer acetate on fatigue in MS patients. Glatiramer acetate was found to be associated with a reduction in absence from work and a significant reduction in fatigue symptoms, as measured by MFIS. The data from Ziemssen et al. were used for the sample size calculation for this study.

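### Randomisation is stratified by site, but the efficacy model does not name site; if site predicts change in fatigue, omitting it makes the test slightly conservative

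*Combined protocol and SAP*

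**What the plan says.** The section on randomisation, treatment assignment and blinding sets the design: "A total of 90 patients will be randomized either to active drug (ACTH), or placebo in a 1:1 ratio stratified by study site". It adds: "Within each site, subjects will be randomized in blocks of 4, 2 ACTH and 2 placebo treated patients". Under Study Design, patients "will be enrolled from five participating sites". Under Patient Recruitment, "full competitive enrollment will be applied until the enrollment goal is fulfilled", so the number at each site is not fixed in advance.

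Under Statistical/Analytical Plan, the primary endpoint is change since baseline in two patient-completed fatigue scales, MFIS and FSS, measured at baseline and weeks 8, 16, 24 and 28. The Statistical method paragraph gives the whole efficacy model in one sentence: "The mixed-effects regression model for the analysis of longitudinal data will be used to test the changes of the fatigue scores over time". It lists no fixed or random effects. Site enters the analysis plan once, for safety: "Summary tables of the AEs will be presented to show the incidence and frequency by treatment group and by study site".

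**The concern.** Blocking within site makes the arms nearly equal in size at every site, so differences between sites largely drop out of the treatment comparison. The usual principle is to analyse as randomised. A model without site leaves any between-site variation in its residual, and the reported standard error then exceeds the true variability of the treatment estimate. The test rejects less often than its nominal level under the null, and some of the precision gained by stratifying is lost.

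This plan does not say whether site is in the model. Besides the possible loss of precision, that leaves the choice open until after the data have been seen. Competitive enrolment adds a practical gap: a site could enrol fewer patients than one block, and there is no rule for handling it.

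**Working it through.** **Inputs from the documents.** Difference in MFIS change 7.6, SD 16.4, 90 patients in total, so 45 per arm (Sample Size Justification). Five sites (Study Design). Two-sided testing at alpha 0.05: "The sample size was calculated by a power analysis for a two-sided test with" alpha 0.05 (Patient Recruitment). The Sample Size Justification prints alpha as 0.5; I use 0.05.

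**Assumed input.** Let ρ be the share of the variance of change explained by site. The documents give no value. I take 0, 2%, 5% and 10%, with 20% as a wider check. The stated SD is treated as the total SD, including any site component.

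**The plan's own power figure.** The standard error of the difference is 16.4 × √(2/45) = 3.457, and 7.6/3.457 = 2.198. A two-sided t-test on 88 degrees of freedom then has power 58.5%, not the stated 87%. The stated figure is reproduced with 90 per arm (87.1%). That is a separate problem; here 58.5% is only the starting point. It assumes no dropout.

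**Size without site.** With balance within site, the true standard error is 3.457 × √(1 − ρ), while a model without site still reports about 3.457. The ratio of reported to true is f = 1/√(1 − ρ), and the true size is 2 × P(Z > 1.96 f).

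**Power.** T′ is a noncentral t variable with noncentrality 2.198 f.
- Without site: P(|T′| > 1.987 f), on 88 df.
- With site: P(|T′| > 1.989), on 88 − 4 = 84 df.

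| ρ | f | 1.96 f | True size without site | Power without site | Power with site |
|---|---|---|---|---|---|
| 0 | 1.000 | 1.960 | 5.0% | 58.48% | 58.44% |
| 2% | 1.010 | 1.980 | 4.8% | 58.6% | 59.3% |
| 5% | 1.026 | 2.011 | 4.4% | 58.7% | 60.6% |
| 10% | 1.054 | 2.066 | 3.9% | 58.9% | 63.0% |

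The gain is about 0.7, 1.9 and 4 points at 2%, 5% and 10%. At ρ = 0 the cost is 0.04 point. At ρ = 20% the true size would be 2.8% and the gain about 9 points.

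**Simulation check.** Permuted blocks of 4 within five sites, 90 patients, a change-score model, 20,000 runs for size and 10,000 for power:
- Equal sites (18 each): size without site 4.8%, 4.4% and 3.9% at ρ of 2%, 5% and 10%.
- Unequal sites (36/22/14/10/8, assumed): 4.9%, 4.4% and 4.0%.
- With site in the model, size was between 4.9% and 5.1% in all six cases.
- Power at ρ = 10% was 59.2% against 63.4% (equal sites) and 59.3% against 63.4% (unequal sites). The simulation error on each power figure is √(0.59 × 0.41/10,000), about 0.5 point.

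**How site must enter.** Write a score as Y = (site level) + (site-by-visit deviation) + other terms. If baseline is one of the repeated outcomes, the treatment effect is a contrast of within-patient differences, Y(visit) − Y(baseline). The site level is common to both and cancels, whether fitted as a fixed effect or a random site intercept. With complete data, such a term leaves the standard error of the treatment-by-time contrast unchanged; only site-by-visit removes the relevant variation. If change from baseline is the outcome, a plain site term does so. The figures above are for the change-score model.

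**The case against.** The strongest objection is that this rests on silence. A reader might infer that the primary model excludes site and that its standard error is therefore too large. The documents support neither step. The method sentence names a class of model and no terms at all: not treatment, visit, baseline or random effects. By the same reading it would also exclude treatment. That part of the objection stands: what can be said is that site is not stated to be in the model.

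Nor is the inflated standard error a fact. It requires site to predict *change* in fatigue. Stable site differences in fatigue level largely cancel in a change score or are absorbed by a patient-level random intercept, and all sites share the same eligibility limits. No between-site variance is given, and at zero there is nothing to correct.

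A reader might also infer from competitive enrolment that patient mix will differ materially between sites. Unequal site sizes do not imply that; they support only the need for a small-site rule.

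Finally, the effect is small over the lower part of the range, its direction is conservative, and it is minor beside the gap between 87% and 58.5% in the same section. All of this lowers the severity. It does not remove the reason to name the randomisation stratum in the model, because adjusting costs almost nothing if site proves irrelevant.

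**Conclusion.** The point holds as a minor one. The randomisation stratum is not among the stated elements of the efficacy model. If site explains 2% to 10% of the variance of change, omitting it would take a nominal 5% test to between 4.8% and 3.9% and forgo roughly 1 to 4 points of power. These sizes rest on the assumed site share, the plan's difference and SD, 45 completers per arm and a change-score analysis. There is no inflation of false positives. The direction of the effect, if site matters, is certain; whether site matters here cannot be judged from the documents.

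**What to change.** In the Statistical method paragraph, list the fixed and random effects of the primary model (MFIS, FSS) and of the secondary efficacy models (BDI-II, ESS, SF-36), and include site as the randomisation stratum:
- If change from baseline is the outcome, add a site term.
- If baseline is one of the repeated outcomes, add site-by-visit. A site main effect or random site intercept alone would not help.

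State that sites enrolling fewer than one full block of 4 are pooled into a single stratum. The rule should use enrolment counts only and be fixed before unblinding.

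The cost is a change of wording and about 4 of 88 error degrees of freedom, which is under 0.1 power point if site has no effect. No new data and no change to the randomisation are needed.

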Review of medical history, physical exam, Modified Fatigue Impact Scale (MFIS), Fatigue Severity Scale (FSS), Epworth Sleepiness Scale (ESS), Beck Depression Inventory-II (BDI-II) and Expanded Disability Status Scale (EDSS) will be performed at screening to assess the eligibility of the patient, and the Columbia-Suicide Severity Rating Scale will be administered. The outcome measures, including MFIS, FSS, BDI-II, ESS, and SF-36, will be administered at baseline, week 8, week 16, week 24, and week 28 which is 4 weeks after the last ACTH or placebo dose. In addition, office visits with the treating physician will be conducted at the same interval for physical exam, review of concomitant medications and adverse events, and monitoring of patient safety and eligibility, and administration of the C-SSR. Laboratory tests will be performed at the time of study visits. A separate serum sample (7 ml SST tube) will be collected at baseline, week 16, and week 28. This sample will be stored at -20c until shipped to the coordinating center. The specimen will then be stored at the study coordinating center for future research use.

STUDY FLOWCHART

ACTH for MS fatigue							
	Screening	Baseline	Follow-up Evaluations				Premature Termination
Visit #	1	2	3	4	5	6	
Week	-4 to -1	0 (±4days)	8 (±4days)	16 (±4days)	24 (±4days)	28 (±4days)	
Informed Consent & Demographics	X						
Randomization		X					
Medical & Neurological History	X	X	X	X	X	X	X
Physical & Neurologic Exam	X	X	X	X	X	X	X
Vital Signs	X	X	X	X	X	X	X
ECG	X						
Laboratory Assessments							
• Urinalysis	X	X	X	X	X	X	X
• CBC	X	X	X	X	X	X	X
• CMP	X	X	X	X	X	X	X
• TSH	X						
• Pregnancy Test/HCG (for female only)	X	X	X	X	X		
Additional Serum Sample for Research Purposes		X		X		X	
EDSS	X						
MFIS, FSS, BDI-II, ESS, SF36	X	X	X	X	X	X	X
C-SSR	X	X	X	X	X	X	X
Study Drug Dispensing		X	X	X			
Protocol Compliance & Study Drug Accountability		X	X	X	X	X	
Concomitant Therapy and AEs	Monitor and record throughout the study						

Informed consent

The investigator or designated research staff will obtain informed consent from each subject after explaining the purpose of the study and the potential risks and benefits known or can be reasonably expected. The IRB approved informed consent form will be signed by the subject or the legal representative before the subject participates in any study procedure. The original signed informed consent form will be kept in the subject's medical record, a duplicate will be provided to the subject.

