The following clinical and laboratory evaluations will occur 16 weeks after baseline with a +/- 4 day window. The investigator/treating neurologist will review inclusion/exclusion criteria to confirm patient eligibility before study drug is dispensed.

- Interval medical and neurological history
- Vital signs
- Physical and neurological exam
- Laboratory assessments: CBC, Urinalysis, CMP, Pregnancy test/HCG (female only)
- MFIS, FSS, BDI-II, ESS, SF36, C-SSR*
- Study drug dispensing
- Protocol compliance study drug accountability
- Concomitant therapy and AEs
- Additional serum sample for research purposes

* The C-SSR must be reviewed by the site principal investigator or treating physician prior to the patient leaving the clinic

Visit 5/Week 24 (24 weeks +/- 4 days from baseline)

The following clinical and laboratory evaluations will occur 24 weeks after baseline with a +/- 4 day window. The investigator/treating neurologist will review inclusion/exclusion criteria to confirm patient eligibility.

- Interval medical and neurological history
- Vital signs
- Physical and neurological exam
- Laboratory assessments: CBC, Urinalysis, CMP, Pregnancy test/HCG (female only)
- MFIS, FSS, BDI-II, ESS, SF36, C-SSR*
- Protocol compliance study drug accountability
- Concomitant therapy and AEs

- Additional serum sample for research purposes

* The C-SSR must be reviewed by the site principal investigator or treating physician prior to the patient leaving the clinic

Visit 6/Week 28 (28 weeks +/- 4 days from baseline)

The following clinical and laboratory evaluations will occur 28 weeks after baseline with a +/- 4 day window.

- Interval medical and neurological history
- Vital signs
- Physical and neurological exam
- Laboratory assessments: CBC, Urinalysis, CMP
- MFIS, FSS, BDI-II, ESS, SF36, C-SSR*
- Protocol compliance study drug accountability
- Concomitant therapy and AEs
- Additional serum sample for research purposes

* The C-SSR must be reviewed by the site principal investigator or treating physician prior to the patient leaving the clinic

Premature termination visit

If discontinuation of study drug occurs, a premature termination visit must be performed as soon as possible, or within 7 days after the last dose of study drug. Randomized patients who were withdrawn from the study for any reason will not be replaced. The following clinical and laboratory evaluations will be performed:

- Interval medical and neurological history
- Vital signs

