- Physical and neurological exam
- Laboratory assessments: CBC, Urinalysis, CMP
- MFIS, FSS, BDI-II, ESS, SF36, C-SSR*
- Concomitant therapy and AEs

* The C-SSR must be reviewed by the site principal investigator or treating physician prior to the patient leaving the clinic

Unscheduled visits

Patients may be asked to return for unscheduled visit to assess any undesired clinical, or laboratory changes that occur during the study.

Study withdrawal

If a patient is lost to follow-up after all means of contact have been attempted, she/he will be withdrawn from the study.

Patient Monitoring and Evaluation

Patients will be instructed to contact their treating neurologist immediately in the event of a relapse.

A Stage 1 safety and efficacy analysis will be performed when 45th subject has completed visit 4(week 16). This analysis will be performed by the unblinded clinical and biostatistician members of the data safety monitoring board (DSMB). While this analysis is being performed, no new subjects may enroll in the investigation, but treatment of those already enrolled will continue while the analysis is taking place. If more subjects in the placebo arm demonstrate 20% or greater improvement than in the ACTH arm on both the MFIS and FSS, the study will be halted and subjects in the study will cease receiving investigational agents. If the ACTH arm is equal or superior to the placebo arm in MFIS and/or FSS, the study will continue, as will recruitment of the additional 45 subjects. If the study is halted due to lack of efficacy after the Stage 1 analysis, an additional analysis for efficacy will be performed utilizing those subjects who completed 6 months enrollment at the time the study was halted.

Treatment compliance

Patients will be instructed to complete a medication administration log and return the logs to study coordinator at each visit. Information on missed doses and total number of missed doses will be captured. Missing more than 2 doses in an 8-week interval is considered non-compliant. The investigator will discuss the medication regimen with non-compliant patients and they will be encouraged to continue with their injection schedule.

Potential Pitfalls and Contingencies

This study requires self-administration of an injectable agent. Thus there is a risk of non-compliance on the part of the subjects either due to needle phobia, intolerance to injections or lapse memory on the part of the subjects.

Data Processing and Analysis

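### No pregnancy test is scheduled at premature termination or Week 28, so women who stop early can leave with recent on-drug time untested; adding HCG there is a cheap safety improvement

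*Combined protocol and SAP*

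**What the plan says.** In the Study Flowchart (section C), the row that begins "Pregnancy Test/HCG (for female only" has marks at screening, baseline and Weeks 8, 16 and 24. The Week 28 and Premature Termination cells are blank, although urinalysis, CBC and CMP are marked in both columns.

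The visit-by-visit lists match. HCG is listed from screening to Week 24. The lists for Visit 6/Week 28 and for the Premature termination visit give only "Laboratory assessments: CBC, Urinalysis, CMP".

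On timing, Laboratory Testing and Study Procedure places "week 28 which is 4 weeks after the last ACTH or placebo dose", so dosing ends at about Week 24. On-treatment visits have a tolerance, for example "16 weeks after baseline with a +/- 4 day window". After early discontinuation, "a premature termination visit must be performed as soon as possible, or within 7 days after the last dose of study drug".

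Other provisions bear on the point:
- Inclusion criterion 6 requires effective contraception.
- Exclusion criterion 17 covers pregnancy, and the exclusion criteria apply throughout the study.
- Pregnancy ends participation (Discontinuation of Subjects from the Study).
- A birth defect is a serious adverse event (section D).
- The Week 28 and termination visits both include "Interval medical and neurological history" and "Concomitant therapy and AEs".

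**The concern.** The plan tests for pregnancy at baseline and at every visit up to Week 24, and it ends participation when a pregnancy occurs. Testing then stops before the whole exposure period is covered. A woman who discontinues between visits has been on drug since her last HCG, and her exit visit does not repeat the test. A completer is tested at about the time of her last dose, when a very recent conception may not yet be detectable, and the Week 28 visit does not repeat the test either.

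A woman with an unrecognised early pregnancy could therefore leave the study without her or the site knowing that it had been exposed to study drug. What is at stake is individual safety and the completeness of the safety record. The efficacy comparison is not involved.

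**Working it through.** The plan states no figure on this point, so there is none to reproduce. The check has two parts: the intervals that follow from the schedule, and a rough size under stated assumptions.

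**Step 1. Intervals (from the visit weeks and the 4-day windows)**

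Days from baseline: Week 8 = 52-60, Week 16 = 108-116, Week 24 = 164-172, Week 28 = 192-200.

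- Longest time from last HCG to last dose for an early stopper: nominally 8 × 7 = 56 days. With windows, 116 − 52 = 64 and 172 − 108 = 64 days.
- Adding the 7 days allowed for the termination visit: 56 + 7 = 63 days nominally, and 64 + 7 = 71 days with windows.
- Completer: the last HCG is on days 164-172 and the last dose is at about day 168. The test precedes the last dose by at most about 4 days.

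**Step 2. Assumptions**

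- From the documents: 20% dropout (Patient Recruitment) and 1:1 allocation.
- Not in the documents, so given as ranges: 30-60 women of childbearing potential; 1-5% yearly contraceptive failure; HCG turns positive 7-21 days after conception; stopping is uniform between visits, so the mean time since the last test is 56/2 = 28 days, or 64/2 = 32 days with stretched windows.

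This gives 24-48 completers and 6-12 early stoppers.

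**Step 3. Expected conceptions with no later scheduled test**

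Formula: women × untested days / 365 × yearly failure rate. Untested days are the mean time since the last test plus the detection lag for early stoppers, and the lag plus up to 4 days for completers.

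| Group | Low | High |
|---|---|---|
| Early stoppers | 6 × (28 + 7)/365 × 1% = 0.006 | 12 × (32 + 21)/365 × 5% = 0.087 |
| Completers | 24 × 7/365 × 1% = 0.005 | 48 × (21 + 4)/365 × 5% = 0.164 |
| Total | 0.010 | 0.25 |

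Half of the total, about 0.005 to 0.13, is on ACTH. Without the window allowances the high total is 12 × 49/365 × 5% + 48 × 21/365 × 5% = 0.081 + 0.138 = 0.22.

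For scale, 24 weeks of dosing give 30 × 1% × 24/52 = 0.14 to 60 × 5% × 24/52 = 1.38 expected conceptions. Most of that time is followed by a scheduled test.

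Per woman, an early stopper has more untested time (35-53 days on average) than a completer (7-25 days). Completers weigh in the total because there are four times as many of them.

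**Step 4. After adding the two tests**

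- Completers: a Week 28 test falls 192 − 168 = 24 to 200 − 168 = 32 days after a last dose on day 168, longer than the 21-day lag, so the remainder is nil. In the extreme case of a last dose on day 172 and a visit on day 192, the interval is 20 days and one day stays uncovered at the longest lag.
- Early stoppers: a termination test 0-7 days after the last dose leaves 0 (7 − 7) to 21 (21 − 0) days uncovered. The remainder is at most 12 × 21/365 × 5% = 0.035.

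**The case against.** The strongest defence is that the pattern looks deliberate. After screening, HCG appears at exactly the visits where the investigator re-checks eligibility (baseline and Weeks 8, 16 and 24), and Week 28 and termination have neither that review nor further dosing. On this reading the test exists to avoid dosing a pregnant woman, and no sentence in the protocol promises to detect every exposed pregnancy. This is a fair explanation of the schedule. It does not close the gap for a woman who stops between visits, and it shows no drawback to testing her. It also fits Week 24 imperfectly, because HCG is done there although no drug is dispensed at that visit.

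Second, the completer part is thin. A woman who conceived by day 168 is at least 24 days past conception at Week 28. With a cycle of about 28 days she would usually have missed a period, and the interval history would bring this out. That stands, and it is why early stoppers are the main concern.

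Third, other safeguards exist: contraception, history, examination, adverse event review and optional unscheduled visits. They reduce the number at risk or catch pregnancies already suspected, but none schedules a test. Women lost to follow-up attend no exit visit, so the fix would not help that part of the 20% dropout.

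A reader might also infer that the protocol has no rule for reporting a pregnancy or following its outcome. The documents do not support that as a finding. A birth defect is already a serious adverse event, with 24-hour reporting and active follow-up, and the case report forms and consent pages, which may hold such a rule, were not available for review.

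**Conclusion.** The gap is real but small. The flowchart and visit lists agree with each other, so this is an incomplete schedule and not an internal contradiction. For early stoppers, up to 56 days on drug (64 with windows) can go untested, and up to 63 days (71) can pass between the last HCG and the termination visit. For completers, only conceptions too recent for the Week 24 test are missed.

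The expected number of conceptions in these windows is about 0.01 to 0.25 in both arms together. That range rests on the assumed number of women at risk, contraceptive failure rate, detection lag and uniform stopping. It is an upper limit on the benefit, since history and adverse event review would catch some cases.

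Two stronger readings should be resisted. The documents give no fetal-risk signal, so the plan cannot be said to leave a known hazard unmonitored. Nor are completers exposed for four untested weeks, because they are off drug from about Week 24. This is a cheap improvement to patient safety, with no bearing on sample size, power or the efficacy analysis.

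**What to change.** Add HCG for women to the laboratory lists for the premature termination visit and Week 28, and mark both cells in the flowchart row. Ask women who stop early to tell the site if a pregnancy is recognised later, since a test within days of the last dose can miss a very recent conception.

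The cost is one extra test per woman (termination or Week 28, not both). That is at most 90 tests and in practice fewer, because men are also eligible. They fall at visits where CBC, CMP and urinalysis are already done. The change needs a routine amendment approved by the Providence IRB and each site's IRB or ethics committee, and no new visit.

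As a query only: ask the sponsor whether the case report or consent forms already say how an exposed pregnancy is reported and followed. If they do, nothing more is needed.
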